9.10 PHARMACOGENETICS ANALYSIS

In order to explore factors that may help explain individual variability in the main PK parameters and safety outcomes, the presence or absence of germline mutations or polymorphisms will be analyzed in leukocyte DNA extracted from a blood sample obtained preferably before treatment start (along with PK sample #1 and the first metabolomics sample of Cycle 1). The influence of known polymorphisms on main PK parameters or safety outcomes will be assessed by a Student's test or a Mann-Whitney's U test as appropriate.

9.11 PHARMACOGENOMICS ANALYSIS

The analysis of potential predictive factors to PM060184 treatment will be analyzed in paraffin-embedded tumor tissue samples from patients participating in the substudy. These factors will include, among others, tubulin isotypes and other factors related to the mechanism of action of PM060184 and to the tumor microenvironment (such as angiogenic factors, and markers of lymphocyte subpopulations and tumor associated macrophages), and their expression will be analyzed at the protein level and/or mRNA level by IHC or quantitative PCR, respectively; their polymorphisms and mutations might also be analyzed, if relevant.

BRAF-mutant-like gene expression subtypes (and potentially full genome expression) will be determined to show potential correlation with response or outcome after treatment with PM060184.

At final study analysis—and if feasible according to overall efficacy and to the number of patients with available biopsy—the subgroup characteristics will be statistically analyzed for correlation with the study efficacy parameters: PFS, ORR, DOR, and OS.

These analyses will include the use of molecular biology techniques to identify and validate PGx markers from pretreatment tumor samples. The basal expression levels of these markers will be correlated with the patient's outcome data. In addition, the experimental data will be analyzed with respect to duration of response and time to disease progression.

Analysis of RNA/protein expression, polymorphisms and mutations will be performed blind, and clinical data compiled only after all analyses are completed. A Fisher's exact test/logistic regression for categorical variables and log rank test/Cox regression for time to event variables will be used to test whether a specific profile is associated with clinical outcome after treatment with PM060184. The prognosis value of markers will be explored for objective clinical response, PFS and OS. In each case, if

applicable, a multivariate model will be developed by stepwise selection. All tests of statistical significance will be two-sided, and significance will be set at 0.05.

10. ADMINISTRATIVE SECTION

10.1 ETHICS

This clinical trial will be conducted in accordance with the ethical principles that have their origin in the World Medical Association (WMA) Declaration of Helsinki ([Appendix 5](#)) and will be consistent with GCP guidelines and pertinent regulatory requirements.

The study personnel involved in conducting this trial will be qualified by education, training and experience to perform their respective task(s).

The study will be conducted in compliance with the protocol. The protocol, any amendments and the patient informed consent will receive IEC/IRB approval/favorable opinion prior to initiation, according to pertinent regulations.

The decision of the IEC/IRB concerning the conduct of the study will be made in writing to the Investigators, and a copy of this decision will be provided to the Sponsor before the beginning of the study.

The Investigator and/or the Sponsor is/are responsible for keeping the IEC/IRB informed of any significant new information about the study drug.

All protocol amendments will be agreed upon by the Sponsor and the Investigator.

Administrative changes of the protocol are minor corrections and/or clarifications that have no impact on the way the study is to be conducted.

10.2 MONITORING, AUDITING AND INSPECTING

The study will be monitored by regular site visits and telephone calls to the Investigator by the clinical trial monitor designated by the Sponsor.

During site visits, the trial monitor should revise original patient records, drug accountability records and document retention (study file). Additionally, the trial monitor should observe study procedures and will discuss any problems with the Investigator.

Adequate time for these visits should be allocated by the Investigator. The Investigator should also ensure that the monitor is given direct access (as per International Conference on Harmonization [ICH] Topic E6 Guideline for Good Clinical Practice, Sections 4.9.7 and 6.10) to source documents (i.e., hospital or private charts, original laboratory records, appointment books, etc.) of the patient which support data entered in the CRFs, as defined in the ICH Topic E6 Guideline for Good Clinical Practice, Sections 1.51 and 1.52.

Systems and procedures will be implemented to ensure the quality of every aspect of the trial.

During the course of the trial, the Sponsor's Clinical Quality Assurance department or designee may conduct an onsite audit (ICH Topic E6 Guideline for GCP, Section 1.6).

Participation in this trial implies acceptance of potential inspection by national or foreign Competent Authorities.

10.3 PATIENT INFORMED CONSENT

The rights, safety and well-being of the trial patients are the most important considerations and should prevail over interests of science and society.

The informed consent process will include all elements required by ICH, GCP and applicable regulatory requirements.

Prior to registration in the trial, the Investigator or a person designated by the Investigator, must provide the patient with one copy of the ICF. This copy must provide written full information about the clinical trial, in a language that is non-technical and easily understood. The Investigator should allow the necessary time for the patient or his/her legally acceptable representative to inquire about the details of the clinical trial; then, the ICF must be freely signed and personally dated by the patient and by the person who conducted the informed consent discussion before the beginning of the study. The patient should receive a copy of the signed ICF and any other written information provided to study patients prior to participation in the trial. Participation in the substudy requires separate consent.

During a patient's participation in the trial, any updates to the consent forms and any updates to the written information will be provided to him/her.

If there is a need to obtain new consent from the patients, the Investigator or a person designated by the Investigator should inform the patients of any new information relevant to the patients' willingness to continue participation in the study, before obtaining the written consent.

10.4 CONFIDENTIALITY/IDENTIFICATION OF PATIENTS

The collection and processing of personal data from the patients enrolled in this clinical trial will be limited to those data that are necessary to investigate the efficacy, safety, quality and usefulness of the study drug used in this trial.

It is the Investigator's responsibility that sufficient information on the identity of the patients be retained.

The trial monitor, the Sponsor's auditor, the IECs/IRBs, and the Competent Authorities should have direct access to all requested trial-related records, and agree to keep the identity of study patients confidential.

The data must be collected and processed with adequate precautions to ensure confidentiality and compliance with applicable data privacy protection laws and regulations.

Explicit consent for the processing of personal data will be obtained from the participating patient before data collection, if applicable, and this consent should also address the transfer of the data to other entities and countries.

The Sponsor shall comply with the Directive 95/46/EEC of the European Parliament and of the Council of 24 October 1995 on the protection of individuals with regard to the processing of personal data and on the free movement of such data.

10.5 ELECTRONIC CASE REPORT FORMS

Electronic case report forms (e-CRFs) will be used to record all data for each patient. It is the responsibility of the Investigator to ensure that e-CRFs are timely, properly and completely filled in, in English. E-CRFs must be completed for all patients who have given their informed consent and have been enrolled into the study.

A patient's source documentation is the patient's records (included but not limited to physician/hospital notes, nurses notes, IMP preparation records including reconstitution and dilution, IMP administration records, QLQs, etc.) and as such, they should be maintained at the study site.

Data collected in the e-CRF will be entered into the Sponsor's databases, which comply with the Spanish Act implementing the Directive 95/46/EC of the European Parliament and of the Council of 24 October 1995 on the protection of individuals with regard to the processing of personal data.

Baseline and off-study visit should be completed for patients registered but never treated.

10.6 INSURANCE

The Sponsor will provide insurance or indemnity in accordance with applicable regulatory requirements.

10.7 RETENTION OF RECORDS

The Investigator/Institution should maintain trial documents according to Section 8 of the ICH Topic E6 Guideline for Good Clinical Practice and as required by applicable regulatory requirements.

Essential documents should be retained as per the aforementioned ICH guideline or for a longer period of time, if required by the applicable regulations.

10.8 USE OF INFORMATION AND PUBLICATIONS

Before the Investigators of this study submit a paper or abstract for publication or otherwise publicly disclose information concerning the study drug or products, the Sponsor must be provided with at least 60 days to revise and approve the proposed publication or disclosure to ensure that confidential and proprietary data are protected.

If the Sponsor determines that patentable patient matter is disclosed in the proposed publication or disclosure, the publication or disclosure will be withheld for a period of time considered convenient. If the study is part of a multicenter study, the first publication of the study shall be made in conjunction with the presentation of a joint, multicenter publication of the study results with the Investigators and the institutions from all appropriate sites that are contributing data, analysis and comments. However, if such a multicenter publication is not submitted within 12 months after conclusion, abandonment or termination of the study at all sites, the present study may be published individually in accordance with the procedure established above.

The order of the coauthors will reflect the relative contribution of each one to study development and analysis. In general, the first author will be the Investigator who recruits the highest number of patients with information finally available for data analysis. Relevant personnel from the Sponsor who have fully participated in the study must be considered for co-authorship of the publication.

12. APPENDICES

Appendix 1. ECOG PERFORMANCE STATUS ASSESSMENT SCALE

Grade	ECOG PS*
0	Fully active, able to carry on all pre-disease performance without restriction
1	Restricted in physically strenuous activity but ambulatory and able to carry out work of a light or sedentary nature, e.g., light house work, office work
2	Ambulatory and capable of all self-care but unable to carry out any work activities. Up and about more than 50% of waking hours
3	Capable of only limited self-care, confined to bed or chair more than 50% of waking hours
4	Completely disabled. Cannot carry on any self-care. Totally confined to bed or chair
5	Dead

*As published in Am. J. Clin. Oncol 5:649-655, 1982: Oken, M.M., Creech, R.H., Tormey, D.C., Horton, J., Davis, T.E., McFadden, E.T., Carbone, P.P.: Toxicity And Response Criteria Of The Eastern Cooperative Oncology Group.

Appendix 2. COCKCROFT-GAULT FORMULA

For Calculated Creatinine Clearance

$$\text{CrCL (mL/min)} = \frac{(140 - \text{Age}) \times \text{Weight (kg)}}{72 \times \text{Creatinine}_{\text{serum}}(\text{mg/dL})} \times 0.85 \text{ if female}$$

Appendix 3. CONTRACEPTION AND PREGNANCY TESTING

This document is based on the Heads of Medicines Agencies' Recommendations Related to Contraception and Pregnancy Testing in Clinical Trials, published by the Clinical Trial Facilitation Group (CTFG) on 15 September 2014 and available at <http://www.hma.eu/ctfg.html> (accessed 1 September 2016)

A woman is considered of childbearing potential (WOCBP) following menarche and until becoming post-menopausal unless permanently sterile. Permanent sterilization methods include hysterectomy, bilateral salpingectomy and bilateral oophorectomy. A postmenopausal state is defined as no menses for 12 months without an alternative medical cause. A high follicle stimulating hormone (FSH) level in the postmenopausal range may be used to confirm a post-menopausal state in women not using hormonal contraception or hormonal replacement therapy. However, in the absence of 12 months of amenorrhea, a single FSH measurement is insufficient. Immediately after detecting a case of suspected pregnancy in a patient, the decision on her continued participation in the clinical trial will be jointly taken by the patient, the Investigator and the Sponsor, with the patient's best interest in mind. A decision to continue the pregnancy will require immediate discontinuation any investigational medicinal product (IMP).

A man is considered fertile after puberty unless permanently sterile by bilateral orchidectomy. Fertile male patients included in this study should refrain from fathering a child or donating sperm during the study and for four months following the last IMP dose. If they have WOCBP partners the male subject should use condom during treatment and for four months following the last IMP dose.

Highly effective birth control methods are:

1. Combined (estrogen and progestogen containing) hormonal contraception associated with inhibition of ovulation ¹:
 - a. oral
 - b. intravaginal
 - c. transdermal
2. Progestogen-only hormonal contraception associated with inhibition of ovulation ¹:
 - a. oral
 - b. injectable
 - c. implantable ²
3. Intrauterine device (IUD) ²
4. Intrauterine hormone-releasing system (IUS) ²
5. Bilateral tubal occlusion ²
6. Vasectomized partner ^{2,3}
7. Sexual abstinence ⁴
8. A combination of male condom with either cap, diaphragm or sponge with spermicide (double barrier methods) are also considered acceptable, but not highly effective, birth control methods.

¹ Hormonal contraception may be susceptible to interaction with the IMP, which may reduce the efficacy of the contraception method (see below).

² Contraception methods that are considered to have low user dependency.

³ Vasectomized partner is a highly effective birth control method provided that partner is the sole sexual partner of the WOCBP trial participant and that the vasectomized partner has received medical assessment of the surgical success.

⁴ Sexual abstinence is considered a highly effective method only if defined as refraining from heterosexual intercourse during the entire period of risk associated with the study treatments. The reliability of sexual abstinence needs to be evaluated in relation to the duration of the clinical trial and the preferred and usual lifestyle of the subject. Periodic abstinence (calendar, symptothermal, post-ovulation methods), withdrawal (coitus interruptus), spermicides only, and lactational amenorrhea method (LAM) are not acceptable methods of contraception. Female condom and male condom should not be used together.

Contraception methods with low user dependency should preferably be used, in particular when contraception is introduced as a result of participation in this trial. It cannot be excluded that the IMP may reduce exposure to substrates of CYP3A through enzyme induction; the efficacy of hormonal contraceptives may be reduced if co-administered with the IMP.

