- 11) Recovery to grade ≤ 1 from any toxicity due to previous therapy (including peripheral sensory/motor neuropathy but excluding alopecia).
- 12) Left ventricular ejection fraction (LVEF) by echocardiography (ECHO) or multiple-gated acquisition (MUGA) scan within normal range (according to institutional standards).
- 13) Evidence of non-childbearing status for women of childbearing potential (WOCBP). WOCBP must agree to use a highly effective contraceptive measure during the trial and up to six months after treatment discontinuation, and fertile male patients must agree to refrain from fathering a child or donating sperm during the trial and up to four months after treatment discontinuation.*

* Valid methods to determine the childbearing potential, adequate contraception and requirements for WOCBP partners are described in [Appendix 3](#).

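### Appendix 3 accepts hormonal contraception alone as highly effective while warning that PM060184 may weaken it, and requires no added or alternative method

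*Protocol*

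**What the plan says.** Protocol Section 4.1, criterion 13 (repeated in the Synopsis) sets the rule for women: "WOCBP must agree to use a highly effective contraceptive measure during the trial and up to six months after treatment discontinuation". A note under the criterion refers to Appendix 3 for what counts as adequate contraception.

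In Appendix 3, under the line "Highly effective birth control methods are", the first two entries are:

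- item 1: "Combined (estrogen and progestogen containing) hormonal contraception associated with inhibition of ovulation" (oral, intravaginal, transdermal);
- item 2: "Progestogen-only hormonal contraception associated with inhibition of ovulation" (oral, injectable, implantable).

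Footnote 1 is attached to both: "Hormonal contraception may be susceptible to interaction with the IMP, which may reduce the efficacy of the contraception method". It points the reader to text further down. That text gives the mechanism, "It cannot be excluded that the IMP may reduce exposure to substrates of CYP3A through enzyme induction", and the consequence, "the efficacy of hormonal contraceptives may be reduced if co-administered with the IMP". The appendix ends there.

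The paragraph holding the warning opens with the only guidance on choosing between methods: "Contraception methods with low user dependency should preferably be used", in particular where contraception is started because of the trial.

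**The concern.** The eligibility rule and the warning concern the same methods, but nothing joins them. A woman using only an oral contraceptive meets criterion 13, although the protocol says the study drug may make that method less reliable. Someone who follows footnote 1 down the page finds the warning explained, not an instruction: no barrier method to add and no method to switch to.

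The stake is fetal exposure. Section 1.2.1 reports that the in vitro genotoxicity work pointed to mutagenicity, Section 4.2 excludes pregnant women, and Section 8.5.3 makes any pregnancy immediately reportable. Contraception is the preventive measure here, and for these women the protocol itself doubts it.

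**Working it through.** No arithmetic beyond counting list entries applies. The check is whether any part of the protocol turns the warning into a duty.

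1. **How many methods must a woman use?** Criterion 13 speaks of a single measure. Any one highly effective entry in Appendix 3 satisfies it.

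2. **Which entries carry the warning?** Counting sub-entries, items 1 to 7 give 11 options: 1a, 1b, 1c, 2a, 2b, 2c, 3, 4, 5, 6, 7. Item 8 (double barrier) is left out because its own text says it is not highly effective. Footnote 1 covers 1a to 1c and 2a to 2c, so 6 of 11 options (6/11 = 55%) are flagged.

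3. **What does the low-user-dependency preference achieve?** Footnote 2 marks 2c, 3, 4, 5 and 6. Four of these five (3, 4, 5, 6) do not carry footnote 1; the implant, 2c, carries both footnotes. Following the preference therefore usually leads away from a flagged method, but not always. It is also only a preference.

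4. **Is there a duty elsewhere?**

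| Place in the protocol | What it covers | Does it close the gap? |
|---|---|---|
| Appendix 3, condom sentence | Male patients with WOCBP partners | No; it does not apply to female patients |
| Section 5.5.4 | Drugs that alter PM060184 metabolism | No; the direction here is PM060184 acting on the contraceptive |
| Schedule of Assessments, footnote 7, and Section 7.4, Table 9 | Pregnancy test each cycle, or at least monthly, on treatment | No; testing detects a pregnancy but does not prevent it |
| Section 8.5.3 | Reporting of pregnancies | No; it applies after the event |
| Section 1.2.1 | In vitro data on CYP450 | It suggests the risk is small, but Appendix 3 does not use it to withdraw the warning |

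5. **Result.** Hormonal contraception alone is sufficient for entry, the protocol says it may be weakened, and no section requires a woman using it to do anything more.

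**The case against.** The strongest reply is that the list and the warning are compatible. A protocol may permit a method and disclose a theoretical interaction. Appendix 3 says only that induction cannot be ruled out, and Section 1.2.1 reports that in vitro studies found little capacity to inhibit or induce CYP450 enzymes. Whether that justifies a mandatory extra method is a risk judgement for the sponsor, who holds the induction data and the Investigator's Brochure. This stands in part. A reader might infer that the appendix contradicts itself, and the text does not support that: a possible loss of efficacy does not negate the listing. What remains is a safety gap, a stated risk with no required response.

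A second reply is that the low-user-dependency preference already responds to the interaction, since it opens the paragraph containing the warning and 4 of the 5 methods it favours are unflagged. That also stands in part, so it would be wrong to say that the protocol does nothing. But the preference does not bind, and it leaves the implant in.

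Two stronger readings should be resisted. One is that the sponsor's registration check would pass such a woman unnoticed. Section 7.2 lets the sponsor refuse registration, and SAP Appendix II includes a listing on contraception; the documents do not say how a woman using only a hormonal method would be handled. The other is a count of affected women. The protocol gives no number of WOCBP and no contraceptive use. Section 1.1 says 90% of colorectal cancers are diagnosed after age 50, which leaves about 10% (100% − 90%), both sexes together, at younger ages. That supports a small number, although it describes cases at diagnosis and not this trial's patients.

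The consent form is not among the documents available, so counselling given there cannot be judged.

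**Conclusion.** The point holds as a minor safety gap. Criterion 13 and Appendix 3 together admit a woman who relies only on a method that the protocol says PM060184 may weaken, and the sole mitigation is a preference that still includes a flagged method.

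Its size is limited. The interaction is possible, not shown, and the in vitro evidence suggests a low risk. The number of women concerned is probably small but is not stated. The added risk of pregnancy cannot be quantified from the documents, because they give neither the degree of induction nor the loss of contraceptive efficacy. The PFS3 hypotheses, the 24- and 60-patient stages, the error rates and all planned analyses are unaffected.

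The conclusion rests on the protocol as written and assumes that no separate instruction to sites or patients already imposes a second method.

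**What to change.** After the CYP3A sentence in Appendix 3, add:

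> *WOCBP using a hormonal method in items 1 or 2 must also use a male condom, or use a method from items 3–7 (which do not carry footnote 1), during the trial and for six months after treatment discontinuation.*

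The six months match criterion 13. That is cautious, since any induction may fade sooner after the last dose.

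One detail needs the sponsor's confirmation. Item 4 is a hormone-releasing intrauterine system. It does not carry footnote 1, but the closing sentence of the appendix refers to hormonal contraceptives generally. The sponsor should state that leaving item 4 unflagged is intended.

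An alternative is to state, with the induction data, that the interaction is not a concern, and to delete footnote 1 and the warning. The added sentence is preferable because it protects women whether or not induction occurs.

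The cost is one sentence at the next amendment and matching patient information. No visits or tests are added, and sample size and analysis stay as they are. The downside is that a few women must add or change a method, and one unwilling to do so could not enrol.
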